Title: Improving Asthma Care Together (IMPACT): A Shared Management Pilot Study

NCT #: NCT04908384

Document Date: 03/19/2020

Statistical Analysis Plan

Data Analysis.

Feasibility. Eligibility, enrollment, and retention (number who complete study) data will be summarized in a study flowchart. A priori feasibility benchmarks include $\geq 60\%$ recruitment (eligible dyads who enroll) and $\geq 80\%$ retention; these benchmarks are based on our previous research (80% recruitment, 86% retention) and similar studies.¹⁰⁶⁻¹¹¹ Study withdrawal reasons and timing will also be reported.

Acceptability. Participants will rate IMPACT acceptability via Acceptability of Intervention (AIM) survey and semi-structured interview. The a priori acceptability benchmark will be $\geq 60\%$ of participants rating IMPACT as acceptable (4 or 5 on AIM, table 3).^{106-108,111} Additional participant acceptability feedback will be documented via an exit interview. Quantitative data will be summarized using descriptive statistics whereas qualitative data will undergo thematic analysis, described above.

Analysis of the primary outcomes (asthma responsibility score, self-efficacy). Descriptive summaries of de-identified data will be transferred into SPSS 24 (IBM Corp, Armonk, NY) for analyses. Distributions of interval and ratio level variables will be checked for normality and transformed as necessary. We will compare characteristics of those who completed the study to those who did not to inform the generalizability of findings. We expect an increase in asthma management responsibility scores and increased dyadic interdependence (i.e. nonindependence of scores between dyads)¹⁰³ between parent and child-reported outcomes over time in the intervention group, suggesting true shared management.

Secondary outcome analyses will use mixed model ANCOVAs to assess whether the primary outcome variable means, adjusted for baseline scores, differ between intervention and control groups. We predict a group x time interaction such that shared management and health outcome variables (asthma responsibility score, self-efficacy, medication adherence, control, QOL) will increase to a greater extent in the intervention group. Also pursuant to Aim 2, the dyadic effect of the intervention will be tested with the Actor-Partner Interdependence Model^{103,112} using structural equation modeling with full information maximum likelihood estimation (FIML). First, the pattern of missing data will be tested to determine if it is missing at random. The FIML method is superior to listwise deletion of missing data points in terms of producing less biased estimates. Next, intraclass correlations (ICC) will be examined for parent and child asthma responsibility, self-efficacy, and general health scores. The APIM produces estimates of actor effects (Person A's pretest \rightarrow Person A's posttest) and partner effects (Person A's pretest \rightarrow Person B's posttest). Actor effects are estimated while controlling for partner effects, and vice versa. In these analyses, dyadic interdependence is indicated by statistically significant **partner effects** (e.g., parent pretest \rightarrow child posttest, controlling for child pretest). Intervention condition will be entered into the model as a dummy coded variable. For each measure taken from both parent and child (i.e., self-efficacy, asthma responsibility) two APIMs will be compared; one in which all of the paths from child variables are constrained equal to their respective paths from the parent variables, and one in which all paths are unconstrained and thus free to vary. Comparison of the fit of these two models indicates whether the effects emanating from the parent are significantly different from those emanating from the child. Parent-child dyads in IMPACT are expected to show stronger **partner effects** than those in the comparison group.

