1. Determine the feasibility, acceptability and initial efficacy of IMPACT with 60 parent-child dyads in an eight-week pilot randomized controlled trial (RCT).

- a. We will use a priori benchmarks to determine the feasibility of IMPACT based on study eligibility, enrollment, and retention.
- b. Acceptability of IMPACT features and engagement will be determined via exit surveys and semi-structured interviews.
- c. Preliminary effect sizes compared to control will be reported on primary outcomes (asthma responsibility, self-efficacy) and secondary outcomes (medication adherence, asthma control and quality of life).
- d. We will also conduct preliminary testing of dyadic interdependence of asthma responsibility over time.

1.6 Study design. Provide a one-sentence description of the general study design and/or type of methodology.

Your answer will help HSD in assigning applications to reviewers and in managing workload. Examples: a longitudinal observational study; a double-blind, placebo-controlled randomized study; ethnographic interviews; web scraping from a convenience sample of blogs; medical record review; coordinating center for a multi-site study.

This study will use a randomized controlled trial design with two parallel study arms, intervention and control (usual care)

1.7 Intent. Check all the descriptors that apply to your activity. You must place an "X" in at least one box.

This question is essential for ensuring that your application is correctly reviewed. Please read each option carefully.

Descriptor
 1. Class project or other activity whose purpose is to provide an educational experience for the researcher (for example, to learn about the process or methods of doing research).
 2. Part of an institution, organization, or program's own internal operational monitoring.
 3. Improve the quality of service provided by a specific institution, organization, or program.
 4. Designed to expand the knowledge base of a scientific discipline or other scholarly field of study, and produce results that: 
• Are expected to be applicable to a larger population beyond the site of data collection or the specific subjects studied, or• Are intended to be used to develop, test, or support theories, principles, and statements of relationships, or to inform policy beyond the study.

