expected lung functioning, spirometers use a reference database that requires patient details including age, gender, height, weight. The parent will be instructed to input the study # (instead of name), year of birth (not date) to avoid unnecessary PHI disclosure. The study team will coach the child through spirometry and request that the results be sent to the study team (via email or text). Note, study team will make every effort to perform spirometry outside (weather permitting) and remain socially distanced and advised to wear masks for spirometry, since it is considered an aerosolizing procedure.

Next, individual data collection will commence. Parent participants will be provided an iPad with the electronic instruments preloaded and instructed to complete the instruments to the best of their ability. If questions arise, the study team will answer as needed. The study team will then work 1:1 with the child and assist with instrument completion (reading items, if requested). This technique has been used successfully in [name] other prior dyadic study designs to preclude parental interference in child items. Full instrument descriptions and timepoints are outlined in table below. Estimated time burden: Parent: 50-55 minutes; Child: 40-50 (plus 30-40 if cognitives added).

Assignment

REDCap randomization module will be used to assign dyads to groups using an externally generated block randomization scheme (stratified by sex). After surveys are complete, the study team will assign dyads to intervention or control by selecting “randomize” within REDCap and proceeding with the following, depending on assignment:

Control

Dyads assigned to the usual care control group will be advised of their assignment. An information sheet will be provided that outlines the upcoming data collection sessions (T1 at 8 weeks and T2 and 16 weeks) with compensation amounts. They will be advised to keep the spirometer to use in future visits, and more frequently if they choose. The PI will send the parent an asthma control assessment, based upon spirometry and asthma status questions (C-ACT), with interpretation using the national asthma guideline standards. This report may be shared with the child's health care provider, if desired. Finally, the family will be advised that at the end of the 16 week study period, they will be offered access to the IMPACT system, including the app and wearable device, should they wish to use it.

Intervention

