The study team (PI, student assistant) will meet with potential parent participants and their child at their home or community library. There, the study team will describe the study and review the consent form with the parent, answering any questions, and emphasizing that their participation is voluntary. An iPad with the preloaded consent form will be provided to the parent for review. Should the parent wish to delay signing the consent form, they may reschedule the T0 visit and will be provided an electronic copy of the form to review.

The parent consent form will include consent for the parent to participate as well as parent consent for their child to participate in the study. Both the parent and child will need to participate in order to be enrolled in the study. The parent will sign via REDCap e-consent module, which will automatically provide an emailed PDF copy of the consent form for parent records.

Remote protocol (due to COVID-19 restrictions or participant family preference)

Remote protocol (if needed): Should remote study visits be required or preferred by participants, a link to the study e-Consent and assent form (with video of the PI reading the assent script) will be sent ahead of time. Families may complete consent and assent asynchronously. If not completed prior to the web conference, the study team will display the REDCap e-Consent module using screen share and allow the parent time to review and complete. Once completed, the study team will read the study assent to the child.

c. **Comprehension.** Describe the methods that will be used to ensure or test the subjects' understanding of the information during the consent process.

Ask if the subject has any questions. Ask the subject to review the basic study procedure, providing prompts if needed (baseline visits, study duration, follow-up visits). Intervention involves weekly online activities, control just visits.

d. **Influence.** Does the research involve any subject groups that might find it difficult to say "no" to participation because of the setting or their relationship with someone on the study team, even if they aren't pressured to participate?

Examples: Student participants being recruited into their teacher's research; patients being recruited into their healthcare provider's research, study team members who are participants; outpatients recruited from an outpatient surgery waiting room just prior to their surgery.

	No

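### Does the 80% retention benchmark need its own IMPACT-arm threshold, and the AIM benchmark a written parent-child rule?

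*SAP*

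**What the plan says.** **Retention.** The SAP, under Feasibility, states: "Eligibility, enrollment, and retention (number who complete study) data will be summarized in a study flowchart". The threshold is at least 80%, and its basis is given as "retention; these benchmarks are based on our previous research (80% recruitment, 86% retention) and similar studies". No arm or completion visit is named. The same paragraph adds: "Study withdrawal reasons and timing will also be reported". Protocol section 1.5, aim 1a, gives the purpose: "We will use a priori benchmarks to determine the feasibility of IMPACT based on study eligibility, enrollment, and retention".

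**What each arm does.** Protocol section 8.2c summarises it: "Intervention involves weekly online activities, control just visits". Under section 5.1, controls are told that "at the end of the 16 week study period, they will be offered access to the IMPACT system".

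**Acceptability.** The SAP benchmark is at least 60% "of participants rating IMPACT as acceptable (4 or 5 on AIM, table 3"). The instrument table in protocol section 5.4 has AIM and its companion feasibility measure, FIM, completed by parent and child at T1, in the intervention group only. Aim 1b adds: "Acceptability of IMPACT features and engagement will be determined via exit surveys and semi-structured interviews". The table 3 that the SAP cites is not in the supplied text.

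**The concern.** Aim 1a speaks of the feasibility of IMPACT, yet half the dyads behind a whole-study retention figure would not use IMPACT during the trial. If the daily check-ins and weekly goal-setting drove families away, good control retention could lift the total over 80%, and the pilot would report its benchmark as met.

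The AIM benchmark has a similar weakness. A pooled figure could reach 60% on the strength of the parents while most children did not find the app acceptable, in a study whose rationale is to give children a part in their own care. A benchmark declared in advance loses force if its unit, its denominator or its definition of a completer can be chosen after the results are in. Protocol section 10.8 adds to the doubt about completers: a dyad that withdraws may continue with assessments, and the SAP does not say whether it then counts as retained.

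**Working it through.** The 80% and 60% figures are chosen thresholds, so there is no calculation in the plan to reproduce. The check asks how often the unwritten details would change the answer.

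**Inputs.** 60 dyads in two arms (protocol sections 1.5 and 1.6). Thresholds of 80% and 60%, and previous retention of 86% (SAP). No allocation ratio is stated, so 30 per arm is assumed, with independent dyads.

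**Counts for retention.** Overall: 0.80 × 60 = 48. IMPACT arm alone: 0.80 × 30 = 24. The overall figure passes with 27/30 control + 21/30 IMPACT = 48/60, where IMPACT stands at 70%. The extreme is 30/30 + 18/30 = 48/60, with IMPACT at 60%.

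**Probabilities.** Let X ~ Bin(30, p_I) be the IMPACT dyads retained and Y ~ Bin(30, p_C) the controls. Overall pass is P(X + Y ≥ 48), IMPACT-arm pass is P(X ≥ 24), and discordance is P(X + Y ≥ 48 and X < 24). Exact binomial sums give:

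| True retention, IMPACT / control | Overall passes | IMPACT arm passes | Overall passes, IMPACT misses |
|---|---|---|---|
| 86% / 86% | 0.931 | 0.883 | 0.075 |
| 80% / 80% | 0.576 | 0.607 | 0.104 |
| 75% / 75% | 0.232 | 0.348 | 0.055 |
| 70% / 70% | 0.057 | 0.160 | 0.016 |
| 75% / 86% | 0.615 | 0.348 | 0.291 |
| 70% / 86% | 0.422 | 0.160 | 0.275 |

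The first four rows assume no difference between arms; the last two assume that IMPACT loses more families. Only there does the discordance become large: 0.291/0.615 = 47% and 0.275/0.422 = 65% of overall passes. The 86% comes from the team's previous research and is cited in support of the benchmarks generally. Using it as a control-arm rate is an assumption, and the documents give no basis for 70% or 75% on IMPACT.

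At equal true rates of 70% to 80%, the IMPACT-arm rule taken alone passes more often than the overall rule (0.160 v 0.057 at 70%), because 30 dyads vary more than 60. At a true 80% it is met with probability 0.607, little better than a coin toss. Requiring both rules when both arms truly retain 86% lowers the chance of passing from 0.931 to 0.931 − 0.075 = 0.856.

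**AIM, rater.** Pooled: 0.60 × 60 = 36 persons. With 24/30 parents (80%) and 12/30 children (40%), 36/60 = 60% passes. At assumed true rates of 80% for parents and 50% for children, with independent ratings, the pooled figure passes with probability 0.841 and a children-only figure (18/30) with 0.181. These rates are illustrative; the documents give none.

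**AIM, denominator.** If 6 of 30 IMPACT dyads give no rating, 15/24 = 62.5% of raters is 15/30 = 50% of those randomised. If all 30 rate, the two coincide.

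**The case for a change.** The strongest case for a change is that the discordance is largest exactly when IMPACT burdens families, which is what a feasibility pilot should detect. Neither the flowchart nor the withdrawal reasons alter the statement that a benchmark was met, and the SAP does not promise either by arm. The remedy would cost only wording, since all the data are already scheduled.

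Part of this stands. The supplied text fixes neither the arm for retention nor the handling of withdrawn dyads that are still assessed. It is also silent on the AIM unit, the AIM denominator and how several items become a score of 4 or 5. Table 3 may settle some of the AIM points but cannot be assumed to.

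The case for a separate threshold is weaker:

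- Aim 1a lists retention beside eligibility and enrollment. Both of those precede randomisation and can only be study-level, so a study-level retention figure belongs with them.
- Retention counts families who complete the study. The visit schedule and the rising payments are common to both arms, although intervention families have extra questionnaires and an interview at T1. A family could drop the app and still be retained, so retention is an indirect measure of intervention burden.
- More direct evidence is already collected: FIM from parent and child in the intervention group, and app usage such as log-ins, goals and progress reports (protocol sections 5.4 and 5.5). The SAP sets no benchmark for either, so they mitigate rather than replace.
- Completion is less open than it seems. Section 5.1 treats study involvement as ended at T2. The mention of a T3 in section 10.8 has no counterpart in the T0 to T2 schedule and reads as a labelling slip.

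**Conclusion.** No change to the plan is needed. Overall retention is a fair benchmark for a pilot trial, and a second threshold on about 30 dyads would add a noisy pass mark more than information. The worrying figures (0.275 to 0.291) depend on an assumed dropout difference of 11 to 16 percentage points. At equal retention the discordance is between 0.016 and 0.104 across the rates examined. All these figures assume 30 dyads per arm and independent dyads.

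The remaining gaps are ones that a competent analyst fills when reporting: a flowchart split by arm, completion taken at T2 with withdrawn-but-assessed dyads shown, and AIM given separately for parents and children with raters beside numbers randomised. Since parent and child each complete AIM, a reader will expect both. The exit interviews with parent and child would also bring out a divided verdict within families. No progression decision depends on either benchmark, so a different reasonable reading would change a descriptive sentence and leave the trial's conduct and between-arm comparisons untouched.

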Dyads assigned to the intervention group will be advised of their assignment. An information sheet will be provided that outlines the intervention tasks (weekly activities) as well as upcoming data collection sessions and compensation amounts. Next, the study team will assist the parent with accessing/downloading the IMPACT app. The family will be encouraged to follow the onboarding screens once downloaded, including pairing the app with the event marker watch (symptom watch) and spirometer device. The symptom watch is a commercially available event marker button that resembles a wristwatch. Children will be taught to press the button when asthma symptoms occur. These events are stored by the watch and synced with the app when connected to the parent phone's Bluetooth.

IMPACT intervention overview:

- Families will be asked to check in on the child's asthma daily (they may use the app to set SMS notifications, if desired) to review symptoms reported by the watch (tracked in the app dashboard).
- They will also be asked to log in weekly to select asthma shared management goals (provided), anticipated barriers, and problem solving. Each subsequent week, dyads will report on their goal progress and select new goals or retain the previous ones.
- To monitor asthma control, families will be prompted to complete the C-ACT (7 item questionnaire) and for the child to complete spirometry. C-ACT and spirometry scores are tracked in the app dashboard (see image)

- The intervention concludes after 8 weeks. The app is configured such that after the 8-week intervention, the goal-setting/monitoring feature is “muted”, but dyads may continue to use the monitoring features (medication use, symptoms, asthma control).

T1 POST-INTERVENTION ASSESSMENT (8 WEEK)

The study team will schedule the T1 data collection session at week 8. The child will be asked to complete spirometry and export results to the study team, as in T0. Dyads will be asked to complete parent and child instruments outlined in the table below, again using the iPads as described above. Families assigned to the intervention will complete short intervention questionnaires and a brief semi-structured interview. Parent: 65-75 minutes; Child: 60-75 (plus 30-40 if cognitives added).

T2 FOLLOW-UP ASSESSMENT (16 WEEKS)

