Asthma control	Childhood Asthma Control Test (C-ACT) (P, C): 7 total items--3 parent (5-point scale) and 4 child (3-point scale)-- assess asthma control, higher scores indicate better control. IC reliability $\alpha=.79$.	<5	X	X	X
	Child spirometry (D) – objective measure of expiratory lung function.² Asthma control (FEV₁:FVC) will follow national spirometry guideline cutpoints.²	5	X	X	X
Asthma-Related Quality of Life	Pediatric Asthma Quality of Life Questionnaire (P, C): 13 items, 7-point scale, parent or child-reported tools measuring quality of life of child/parent of child with asthma. Higher scores indicate higher QOL.	<5	X	X	X
OPTIONAL COGNITIVE BATTERY – in person only					
Executive Functioning	NIH Toolbox Cognition Battery (C): 30 min battery measures attention, processing speed and working memory in game-like format. Validated for ages 3-15 years, administered via iPad.	30-40	X	X	X
IMPACT Usability & Acceptability					
Acceptability	Feasibility and Acceptability of Intervention Measures (FIM, AIM) (P, C): 8 items using 5-point scale; higher scores indicate higher feasibility or acceptability. Established validity, reliability.	<5		I	
Usability	System Usability Scale (P): 10-items, 5-point scale to report usability of system. Higher scores indicates higher usability. Established validity, reliability.	<5		I	
Overall	Semi-structured Interview (P,C): 12 semi-structured questions to be used in post-intervention interview with parent and child.	10-15		I	
(P) Parent report, (C) child report, (D) direct measurement; I= intervention group only; C= control group only					

5.5 Data sources. For all types of data that will be accessed or collected for this research: Identify whether the data are being obtained from the subjects (or subjects' specimens) or whether they are being obtained from some other source (and identify the source).

If you have already provided this information in Question 5.1, you do not need to repeat the information here.

Direct measurement: child weight, height, spirometry, NIH Cognitive battery (optional)

Self-report: all surveys/questionnaires

IMPACT app use – site tracks unique ID logon date, time, duration, use (goals selected, progress, asthma symptom reports, asthma control – C-ACT and spirometry, medication use)

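### The 60% acceptability benchmark has no stated denominator, and AIM is collected only at T1, so IMPACT families who leave before T1 have no rating and the default percentage probably runs high

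*SAP*

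**What the plan says.** The SAP (Data Analysis, Acceptability) sets the threshold at 60% or more "of participants rating IMPACT as acceptable (4 or 5 on AIM, table 3". It does not define participants, does not say whether the unit is the parent, the child or the dyad, and does not say how a missing rating counts. Quantitative acceptability data are to be summarised descriptively. The table it points to is not in the public SAP; the instrument table in Protocol 5.4 is the only one available.

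That table lists "Feasibility and Acceptability of Intervention Measures (FIM, AIM) (P, C): 8 items using 5-point scale", so both parent and child rate. It carries a single mark, in the T1 column, and its footnote reads "I= intervention group only". Protocol 5.1 agrees in its T1 description: "Families assigned to the intervention will complete short intervention questionnaires and a brief semi-structured interview".

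Three other provisions bear on the point:
- The SAP (Feasibility) has a separate retention benchmark of 80%, with retention glossed as "retention (number who complete study", and cites "our previous research (80% recruitment, 86% retention". It also promises a flowchart and the reasons for and timing of withdrawals.
- The SAP compares completers with non-completers. Full information maximum likelihood is named for the actor-partner model only, not for AIM.
- Protocol 10.8 says that people who withdraw will be asked to continue assessments, but labels these T2 and/or T3. The trial's visits are T0, T1 and T2.

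**The concern.** Acceptability is part of the trial's aim (Protocol 1.5), and this is one of only three numeric benchmarks in the SAP. A family with no T1 visit has no AIM rating. With no missing-data rule, a descriptive summary would naturally be a percentage of the surveys returned.

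Families who dislike IMPACT are plausibly the most likely to leave early. The percentage would then be conditioned on attendance, which acceptability itself affects, and the probable direction of the bias is upward. Because the denominator is open, whether a borderline result meets 60% could also turn on a choice made after the data are seen.

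**Working it through.** The plan offers no derived figure to reproduce: 60% is a chosen threshold with no sample size or error rate behind it. The check is how that threshold behaves under the two denominators that the wording allows.

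**Inputs**
- Threshold 60%: SAP, Acceptability.
- 60 dyads: Protocol 1.5. The allocation ratio is not stated (Protocol 5.1, Assignment). Assumed 1:1, so N = 30 IMPACT dyads.
- T1 attendance in the IMPACT arm: not given. I use 80% (the SAP's retention floor) and 86% (the team's earlier retention). Both describe study completion across the whole trial, so applying them to T1 in one arm is an assumption.
- Unit: not given. One reporter per dyad is assumed.

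**Formulas**
- Raters: m = N × attendance, rounded.
- Smallest count that meets the benchmark among raters: k = 0.60 × m, rounded up.
- Share of those assigned who are known to endorse: k/N.
- Share if every non-rater would also have endorsed: (k + N − m)/N.
- Count needed when missing is treated as not acceptable: 0.60 × 30 = 18.

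| Attendance | m | k | k/m | k/N | (k + N − m)/N | 18/m |
|---|---|---|---|---|---|---|
| 80% | 24 | 14.4 → 15 | 62.5% | 15/30 = 50.0% | 21/30 = 70.0% | 75.0% |
| 86% | 25.8 → 26 | 15.6 → 16 | 61.5% | 16/30 = 53.3% | 20/30 = 66.7% | 69.2% |
| 100% | 30 | 18 | 60.0% | 60.0% | 60.0% | 60.0% |

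**Where the denominator decides the result.** With 24 raters, 15, 16 or 17 endorsements meet 60% of raters but miss 18 of 30. With 26 raters, 16 or 17 do.

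**Sensitivity to the assumptions, at 80% attendance**
- Counting parents and children as individuals: 60 assigned, 48 raters, 0.60 × 48 = 28.8 → 29, and 29/60 = 48.3%.
- Enrolling up to the 65 allowed in Protocol 2.8, hence 32 or 33 IMPACT dyads: 26 raters, k = 16, giving 16/32 = 50.0% or 16/33 = 48.5%.

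The result at the retention floor stays close to one half under each of these choices.

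**The case against.** The strongest reply is that the SAP never restricts the benchmark to raters. Its phrase about rating IMPACT as acceptable can be read as describing the numerator, with all IMPACT participants as the denominator. That stands. A reader might infer that the plan adopts a raters-only rule; the text does not say so, and the defect is that the denominator is undefined.

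Second, stopping the app is not the same as missing T1. The T1 questionnaires go to families assigned to the intervention, the T1 payment is for completing the visit (Protocol 4.4), and Protocol 10.8 asks withdrawers to continue. This narrows the concern to families who do not attend T1. It does not remove it: continuing is optional, AIM is scheduled at no other visit, and the labels in 10.8 do not name T1. If those labels come from numbering the visits from 1, week 8 would be covered, but the text does not show that.

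Third, dropout is visible through the retention benchmark, the flowchart, the withdrawal reasons and the completer comparison. That also stands, but none of these changes the acceptability percentage. Retention is not set by arm, so losses concentrated in the IMPACT arm could be diluted in the trial-wide figure.

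Fourth, counting a missing rating as not acceptable mixes retention with acceptability, which the SAP measures separately, and families miss visits for unrelated reasons. This is a fair argument against making it the only rule. It is no argument against showing both figures.

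**Conclusion.** The point holds as an undefined denominator combined with T1-only collection in one arm. Under 1:1 allocation, one reporter per dyad and 80% T1 attendance in the IMPACT arm, a raters-only figure can meet the benchmark with 50% of those assigned known to endorse IMPACT. At 86% attendance it is 53%. If nobody misses T1 the gap disappears. The upward direction is likely rather than certain, since it depends on dissatisfied families leaving more often.

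Two stronger conclusions are tempting and unsupported. A reader might infer that IMPACT could be declared acceptable although most assigned families rejected it. Non-raters have not called it unacceptable: 50% and 53% are lower bounds, and the share who would endorse could be as high as 70% or 67% in the same two cases. A reader might also treat the benchmark as a formal rule for proceeding to a larger trial. The documents call it an a priori benchmark and attach no progression decision to it.

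**What to change.** In the SAP:
- Define the denominator as all participants randomised to IMPACT, and report parents and children separately.
- Report two percentages side by side: missing AIM counted as not acceptable, and raters only. Describe the benchmark as robustly met only if both reach 60%.

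In the protocol:
- Offer AIM at withdrawal to dyads who leave before T1.
- Reconcile the visit labels in section 10.8 with the T0, T1, T2 schedule so that T1 is clearly covered.

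The cost is small. The SAP changes are wording only. The protocol change adds a questionnaire listed at under 5 minutes for families who withdraw, and no extra sample is needed. The real price is a less favourable figure: at 80% attendance, 18 of 24 raters (75%) must endorse IMPACT for both percentages to reach 60%.
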